3. OVERALL CLINICAL STUDY DESCRIPTION

This is a phase 3, multicenter, open-label study to evaluate the safety of QM1114-DP for the long-term treatment of moderate to severe GL and LCL.

Eligible subjects will receive up to 4 treatments of QM1114-DP in the GL and/or LCL and will be monitored for safety and efficacy over a period of up to 52 weeks.

The first treatment will be administered at Day 0 (Baseline). Re-treatments can be administered at any of the follow-up visits from Week 12 to Week 40, provided that the subject is eligible for retreatment and there has been at least 12 weeks since the last treatment. Follow-up visits for treated subjects are conducted at Day 7 and Day 14 after each treatment. Follow-up visits, i.e. not treatment dependent, are scheduled at Week 4, 8, 12, 16, 20, 24, 28, 32, 36, 40, 44, 48 and 52.

To ensure a sufficient amount of long-term safety data is included in the database per ICH E1 guidelines, approximately 900 subjects will be enrolled; all subjects will be followed for at least 24 weeks and at least 300 subjects will be followed up to 52 weeks. The study may be stopped when at least 300 subjects have completed the Week 52 study visit.

All subjects that meet the eligibility criteria and are enrolled in the study will be treated on Day 0. Additional treatment can be administered at any of the follow-up visits from Week 12 to Week 40, provided that the following criteria are met:

- It has been at least 12 weeks since the previous treatment.
- Moderate (grade 2) or severe (grade 3) GL and/or LCL at maximum contraction (i.e., frown and smile, respectively) as assessed by the Investigator CCI (ILA CCI). In order to treat LCL, both sides should meet severity criteria and be treated at the same visit.
- There are no ongoing adverse events assessed as related to the treatment, which could exclude the subject from re-treatment.
- Subject agrees to receive re-treatment.
- If the subject is a female of child bearing potential, must be willing to take a pregnancy test
 and the result must be negative in order to receive re-treatment.
- There is no other medical or surgical condition that would put the subject at undue risk in case he/she receives an additional treatment cycle, according to Investigator's judgment.

After each treatment, subjects will return for study visits at Day 7 and Day 14. Follow up visits, i.e. not treatment dependent, are scheduled at Week 4, 8, 12, 16, 20, 24, 28, 32, 36, 40, 44, 48, and 52.

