5.2 Clinical Study Population Characteristics

In order to be eligible for the clinical study, subjects must fulfill all of the following criteria. These criteria are applicable at both screening and baseline unless otherwise specified.

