- 16. Planned facial surgery, eye surgery (including LASIK procedure) or aesthetic procedures (e.g. ablative skin resurfacing, laser treatment, micro needling, chemical peel, botulinum toxin treatment, or dermal fillers) in the face during the study period.
- 17. History or presence of facial nerve palsy, or any medical condition that may put the subject at increased risk with exposure to botulinum toxin including diagnosed myasthenia gravis, Lambert-Eaton syndrome, amyotrophic lateral sclerosis, or any other condition that might interfere with neuromuscular function.
- 18. Use of medications that affect neuromuscular transmission such as curare-like depolarizing agents, lincosamides, polymyxins, anticholinesterases, and aminoglycoside antibiotics.
- 19. Subject with bleeding disorder or subject currently using anticoagulants.
- 20. Subject has any prior or current psychiatric illness (e.g. Psychosis, depression, anxiety), alcohol or drug abuse, or is taking antidepressant, anxiolytic, or antipsychotic medication that, in the Investigator's opinion, could affect the subject's safety and/or participation in the study.
- 21. Other concurrent medical conditions, therapy, or other condition that, in the Investigator's opinion, would interfere with the evaluation of the study medication, safety or efficacy, and/or put the subject at risk if he/she participates to the study.
- 22. Participation in an investigational device or drug study within 30 days prior to study treatment or plans to enroll in any other investigational study during participation in this study.
- 23. Study center personnel, close relatives of the study center personnel (e.g. parents, children, siblings, or spouse), employees or close relatives of employees at the Sponsor company.

	43QM1903 Clinical Study Protocol - QM1114 - LTS for LCL/GL	Dec id
♣ GALDERMA	To an action of the state of th	MA-40372

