5.4.3 Recording

Previous and concomitant therapies are to be recorded in the subject's source documents and eCRFs

Concomitant therapies are to be reviewed at each visit and updated in the source documents and eCRFs as needed.

Any new concomitant therapy or modification of an existing therapy may be linked to an AE. A corresponding AE form should be completed to account for the change in therapy, except in some cases such as therapy used for prophylaxis, dose modification for a chronic condition, etc.

	Title	Doc id
• GALDERMA	43QM1903 Clinical Study Protocol - QM1114 - LTS for LCL/GL	MA-40372

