5.4.4 Authorized Concomitant Therapies

Unless listed in prohibited concomitant therapies (see Section 5.4.5), all are authorized.

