5.4.5 Prohibited Concomitant Therapies

The following therapies are prohibited because they may interfere with the efficacy and/or safety assessment of the study product.

- · Botulinum toxin of any serotype.
- Any other investigational new drug or device.
- · Any absorbable (temporary) or non-absorbable (permanent) material in the treatment areas.
- Facial aesthetic procedures (e.g., ablative skin resurfacing, laser treatment, micro needling, photodynamic therapy, tattooing or chemical peel) or any other procedures in the treatment area.
- · Facial surgery and eye surgery (including LASIK procedure).
- Medications that affect neuromuscular transmission such as curare-like depolarizing agents, lincosamides, polymyxins, anticholinesterases and aminoglycoside antibiotics.

If a prohibited therapy becomes a necessary treatment for best clinical interest of the subject or due to safety reason, the Medical Monitor (Section 11.9) should be notified, if time permits, to discuss possible alternatives prior to administration of a prohibited therapy.

If a subject receives a prohibited therapy during the clinical study, the Medical Monitor (Section 11.9) should be notified to discuss the subject's continuation in the clinical study.

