6.1.6.3 Treatment Regimen

Subjects will receive up to four treatments with QM1114-DP in their glabellar and lateral canthal lines during the study period, each treatment cycle is at least 12 weeks apart. Follow-up assessments for treated subjects are conducted at Day 7 and Day 14 post-treatment. All subjects are followed up every 4th week for a period of up to 52 weeks.

The following conditions are required to be met for re-treatment post-baseline:

- · It has been at least 12 weeks since the previous treatment in the intended area
- For GL re-treatment:
 - Moderate (grade 2) or severe (grade 3) rhytides at maximum frown as assessed by the Investigator (ILA).

CCI

- For LCL re-treatment:
 - Moderate (grade 2) or severe (grade 3) rhytides at maximum smile as assessed by the Investigator (ILA).

CC

- In order to treat LCL, both sides should meet severity criteria and be treated at the same visit.
- There are no ongoing adverse events assessed as related to the treatment, which could
 preclude the subject from re-treatment.
- Subject agrees to receive re-treatment.
- If subject is a female of child-bearing potential, agrees to take a pregnancy test and test result
 must be negative in order to receive re-treatment.
- There is no other medical or surgical condition that would put the subject at undue risk in case he/she receives an additional treatment cycle, according to investigator's judgment.

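### Anticoagulant use is an absolute bar before the first treatment but a matter of investigator judgment before treatments 2 to 4

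*Protocol*

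**What the plan says.** **Entry.** Exclusion 19 (Protocol 5.2.2, repeated in the synopsis) reads "Subject with bleeding disorder or subject currently using anticoagulants". Unlike exclusions 15, 20 and 21, it has no clause leaving the matter to the investigator's opinion. Section 5.2 makes the criteria "applicable at both screening and baseline unless otherwise specified", and Table 1 schedules the inclusion/exclusion review at those two visits only.

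**During the study.** Section 5.4.4 states: "Unless listed in prohibited concomitant therapies (see Section 5.4.5), all are authorized". The list in 5.4.5 includes "Medications that affect neuromuscular transmission such as curare-like depolarizing agents" and similar drugs, which carries exclusion 18 forward, but it does not include anticoagulants. Contact with the Medical Monitor is tied to prohibited therapies.

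**Re-treatment.** Section 3 allows re-treatment at Weeks 12 to 40 "provided that the following criteria are met", and 6.1.6.3 gives the matching list:
- the 12-week interval
- grade 2 or 3 severity
- no ongoing related adverse event that stands in the way
- the subject's agreement
- a negative pregnancy test where applicable
- "There is no other medical or surgical condition that would put the subject at undue risk", as the investigator judges

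Neither list names a medication or refers back to the exclusion criteria.

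**Knowledge of the drug.** Section 5.4.3: "Concomitant therapies are to be reviewed at each visit".

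**The concern.** The same product goes into the same sites at every treatment. Whatever led the sponsor to refuse anticoagulant users on Day 0 applies equally at Weeks 12 to 40. Yet a subject who would have been turned away on Day 0 can receive further elective facial injections while on the drug, if the investigator sees no undue risk.

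Two things are at stake. The first is protection of the few subjects concerned. The second is consistent handling, since up to 36 centers would each decide without a written rule. The primary endpoint is the incidence and severity of treatment-emergent adverse events, so the size of any effect on those rates also needs checking.

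**Working it through.** The plan gives no figure to reproduce, so the check is a reading of the text followed by a bound on the size.

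**Path of a subject who starts an anticoagulant after Day 0**
1. Exclusion 19 no longer applies, because 5.2 limits it to screening and baseline.
2. The drug is authorized: it is not in 5.4.5, so 5.4.4 allows it. No Medical Monitor discussion is required.
3. At Visits 5 to 12, Section 8.1.4 asks only whether the re-treatment criteria are met.
4. Of those criteria, only the last can stop re-injection because of the drug, and it does so by judgment.

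The redacted lines in the re-treatment lists sit with the severity criteria, which is an unlikely place for a medication rule.

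**Exposure, from the protocol**
- Injections per full re-treatment: 5 (6.1.6.1.1) + 6 (6.1.6.1.2) = 11.
- Most re-treatments that fit, with visits every 4 weeks from Week 12 to 40 and at least 12 weeks between treatments:
  - first at Week 12 or 16: 3 re-treatments, 3 × 11 = 33 injections
  - first at Week 20, 24 or 28: 2 re-treatments, 22 injections
  - first at Week 32, 36 or 40: 1 re-treatment, 11 injections

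**Assumptions, not in the protocol**
- 0.5% to 2% of 900 subjects start an anticoagulant: 0.005 × 900 = 4.5 to 0.02 × 900 = 18.
- Starts are spread evenly over 52 weeks, the drug is continued, and all starters are followed to Week 52.

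A re-treatment at week w is then given on the drug with probability w/52. The mean number on the drug per starter is the sum of the re-treatment weeks divided by 52.

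| Re-treatment weeks | Mean per starter |
|---|---|
| none | 0 |
| 12 | 12/52 = 0.23 |
| 28 | 28/52 = 0.54 |
| 20, 40 | 60/52 = 1.15 |
| 12, 24, 36 | 72/52 = 1.38 |
| 16, 28, 40 | 84/52 = 1.62 |

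The last row is the largest sum that the schedule permits. The rows for 28 and for 20 and 40 correspond roughly to the 4 to 6 months of effect in Section 1.1. The whole study therefore has from 0 to 18 × 84/52 = 29.1 re-treatments on the drug. Early stopping, which Section 4 allows once 300 subjects have completed Week 52, would lower the upper end.

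**Effect on adverse event rates**

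Assume further that the drug adds 10 to 30 percentage points of bruising risk (not in the protocol). The shift in the rate of a re-treatment cycle is the share of subjects on the drug times that increase:
- low: 0.5% × 12/52 = 0.12%; × 10 points = 0.01 points
- middle: 1% × 26/52 = 0.5%; × 20 points = 0.10 points
- high: 2% × 40/52 = 1.54%; × 30 points = 0.46 points

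**The case against.** The strongest reply is that nothing here is contradictory. Entry criteria and re-treatment criteria are separate lists, many other exclusions are not repeated at re-treatment, and stricter entry than re-treatment is a normal design. An anticoagulant is usually prescribed for a medical condition, so the last re-treatment item covers the case. The drug is seen at the visit review, the investigator may discontinue a subject for safety (5.5), and the sponsor may end a subject's participation.

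Much of this stands. A reader might infer that the last item cannot reach a medication, because exclusion 21 covers "Other concurrent medical conditions, therapy, or other condition that" while the re-treatment item speaks only of a condition. The wording does differ, but it does not support so narrow a reading: an investigator can reasonably apply the item to a subject on a new anticoagulant. What remains is that the item gives discretion where exclusion 19 gives none.

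A reader might also infer an oversight. Exclusions 1, 2, 8, 9, 16, 18, 19 and 22 bar a therapy outright, and all but 19 have a counterpart in 5.4.5. The count is soft, since exclusions 1 and 2 share one line of 5.4.5 and 8 and 9 share another. Leaving anticoagulants off that list also fits a deliberate choice not to prohibit a drug that may be medically necessary. The protocol does not show which it was.

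A last objection is that an absolute bar would be stricter than the rule for prohibited drugs, which leads to a Medical Monitor discussion of continuation. That is true. But it restores only what exclusion 19 already requires on Day 0, and it restricts elective injections, not the drug.

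**Conclusion.** The point holds as a minor one. An absolute bar before treatment 1 becomes a judgment before treatments 2 to 4, with no reason given for the difference and no rule to keep up to 36 centers consistent. It would be wrong to say that re-injection is ungoverned: the last re-treatment item applies, and the investigator will usually know of the drug.

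The number affected is small: 0 to 1.62 re-treatments on the drug per starter, and 0 to about 29 in the study, under the assumed uptake of 0.5% to 2%, even spread of starts, continued use and full follow-up. The shift in adverse event rates, 0.01 to 0.46 points in the cases shown, also rests on an assumed bruising increase and is negligible for the primary endpoint. The protocol states neither an uptake rate nor a bruising risk. The case for change rests on subject protection and consistency, not on bias.

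**What to change.** Add one condition to the re-treatment lists in Section 3 and 6.1.6.3: *Subject is not currently using an anticoagulant.* State that such subjects remain in follow-up without injections while on the drug. The protocol already has a model for this in 7.2.5.2.3, where a pregnant subject may continue visits without dosing. Leave 5.4.5 unchanged, because an anticoagulant may become medically necessary. If the sponsor does intend judgment after Day 0, the protocol should say so for anticoagulants explicitly.

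The cost is one line in each of two sections. No new data are needed, since concomitant therapies are already reviewed at every visit. The downside is that the re-treatments counted above would be forgone. The 24- and 52-week follow-up counts are not affected, because these subjects stay in the study.

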6.2 Study Product Packaging and Labeling

QM1114-DP is manufactured under aseptic conditions.

The labels will be printed in English. The text of the label will detail the information requested by Good Manufacturing Practice and local regulations, and at a minimum include the protocol number, storage conditions, and an investigational test article disclaimer ("Caution: New Drug - Limited by Federal (or United States) law to investigational use.")

	Title	Dec id
♣ GALDERMA	43QM1903 Clinical Study Protocol - QM1114 - LTS for LCL/GL	MA-40372

6.3 Supplies Management

6.3.1 Accountability

Upon receipt of the study product, the Investigator or designee will maintain accurate records of the study product delivery to the clinical study center, the inventory at the clinical study center, the use by each subject, the reconciliation of all study product received from the Sponsor's designee, and the return to the Sponsor's designee for disposal of unused study product.

All study product sent to the Investigator/Institution will be accounted for and no unauthorized use is permitted.

6.3.2 Storage of Study Product

Study product must be stored in a safe and secure area with restricted access, under the storage conditions specified by the Sponsor (see Table 2).

6.3.3 Dispensing and Return

All study product must be inventoried and a record of the dispensing for each subject must be appropriately documented. Any dispensing errors must be reported to the Sponsor/CRO and properly documented.

Unused or expired study product will be returned for destruction to the Sponsor representative at time points approved by the Sponsor.

In the event of early termination/suspension of the clinical study, a rapid recall of study product will be initiated.

6.3.4 Treatment Compliance Management and Record

The treatment is an injection administered by the Investigator. Details of the injection procedure will be recorded in the eCRF and subject source documents. No other measurements of treatment compliance will be made.

6.3.5 Dose Modification

Dose modifications are not permitted.

6.3.6 Product Quality Complaints

Product Quality complaints (PQCs) should be reported to the Safety e-mail listed in Section 11.9.

A PQC is an external judgement presuming a quality defect of a product; quality issue for a product relating to its presentation or use, identified by a subject, a practitioner or Investigator site CONFIDENTIAL

personnel, a distributor, or anyone else involved in clinical supplies handling. Examples may include but are not limited to appearance issues, odor, damaged stoppers, low fills, and foreign matter in the product. These complaints may or may not represent a potential risk to the subject. A PQC form must be completed by the study center personnel and forwarded to the Sponsor or designee within 24 hours of awareness. Affected study product should be quarantined, and not used, until further notice by the Sponsor.

Additional contact details are provided in the Investigator's site file.

6.4 Blinding

Not applicable. This is an open-label study.

6.4.1 Verification of Blinding

Not applicable. This is an open-label study.

6.4.2 Unblinding During the Clinical Study

Not applicable. This is an open-label study.

7. CLINICAL STUDY ASSESSMENT

7.1 Efficacy Assessments

7.1.1 Investigator 4-point Photographic Scale of Glabellar Line Severity (GL-ILA)

The validated Investigator 4-point Photographic Scale of Glabellar Line Severity (GL-ILA) (Appendix 1) includes two grading systems: one for Investigator live assessments at maximum frown, and one for Investigator live assessments at rest. The scale represents the severity of glabellar lines from none (grade 0), mild (grade 1), moderate (grade 2) to severe glabellar lines (grade 3). Each grade is also depicted by an individual photograph and a descriptive text. The Investigators will be trained on the use of the 4-point Photographic Scale.

The Investigators will use the 4-point Photographic Scales for direct, live comparison with the subject's face at rest and maximum frown respectively, at screening, baseline (prior to treatment), and at all post-baseline visits (prior to treatment, as applicable).

	Title	Dec id
♣ GALDERMA	43QM1903 Clinical Study Protocol - QM1114 - LTS for LCL/GL	MA-40372

7.1.3 Investigator 4-point Photographic Scale of Lateral Canthal Line Severity (LCL-ILA)

The validated Investigator 4-point Photographic Scale of Lateral Canthal Line Severity (LCL-ILA) (Appendix 2), developed by Galderma, includes two grading systems: one for the Investigator live assessments at maximum smile, and one for the Investigator live assessments at relaxed position. The scale represents LCL severities from none (grade 0), mild (grade 1), moderate (grade 2), to severe (grade 3). Each grade is also depicted by an individual photograph and descriptive text. The Investigators will be trained on the use of the LCL-ILA.

The Investigators will use the LCL-ILA for direct, live comparison with the subject's face for grading LCL severity at screening, baseline (prior to treatment), and at all post-treatment visits. Left and right LCL should be assessed separately at relaxed position and maximum smile.

CCI	
CCI	
CCI	
CCI	
CCI	

8-26 19:44

43QM1903 Clinical Study Protocol - QM1114 - LTS for LCL/GL

Doc id

7.2 Safety Assessments

Safety assessments will be conducted for all subjects at the time points indicated in Schedule of Assessments (Table 1). Safety parameters include an evaluation of AEs, FPE, vital signs, laboratory safety tests (chemistry and hematology), and neutralizing antibody production.

7.2.1 Focused Physical Examination (FPE)

At the time points indicated in the Schedule of Assessments (Table 1), the Investigator or designee will perform a physical examination of the subject that includes the face, head, and neck. Further details are provided in Appendix 5.

Post-baseline, the signs and symptoms will also be monitored via physical examination of face, head, and neck to evaluate local effect of toxin. In addition, general physical examination to evaluate the remote spread events will be conducted. The list of remote spread of toxin events is considered while doing clinical evaluations based on subject's symptoms and signs (Appendix 6). Directed questioning and examination will then be performed as appropriate.

The Investigator may choose to investigate any other sign that he/she observes during the physical examination. Abnormalities noted pre-injection, i.e. at the screening/baseline visits, should be recorded as medical history and abnormalities noted post-injection should be recorded as AEs.

7.2.2 Vital Signs

At the time points indicated in the Schedule of Assessments (Table 1), evaluation of vital signs shall be performed after approximately 10 minutes rest in the sitting position. It shall include measurement of systolic and diastolic blood pressure, heart rate, and respiratory rate. Vital signs will be taken prior to any blood draw, excluding post-treatment measurements on Day 0.

All abnormal values at the baseline visit identified, as clinically significant by the Investigator, shall be recorded in the Medical History form.

For any clinically significant changes from the baseline visit, an AE is to be recorded.

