- Screening and baseline visits may be on the same day. If completed on the same day, only perform study assessments once (i.e., PE, UPT, SLA, ILA, AE, concomitant therapies/procedures, inclusion/exclusion review)
- 2. Includes date of birth, gender, race, ethnicity, height, and weight.
- 3. To be performed before treatment (as applicable post-baseline if re-treatment performed).
- To be performed before treatment and post-treatment (as applicable post-baseline if retreatment performed).
- To be performed only if female of childbearing potential and eligible for treatment.

- Vital signs are taken seated after 10 minutes rest.
 Vital signs are taken prior to any blood draw (excluding post-treatment measurements on Day 0).
- 7. Following treatment administration, subjects will be monitored at the study center for 30 minutes.
- Only if subject meets re-treatment criteria.
- 9. If the subject withdraws before the final visit the ET visit should be completed, if possible.
- 10. Week 12, 16, 20, 24, 28, 32, 36 and 40.
- Blood sample for serum antibody testing if subjects are eligible for re-treatment: before each re-treatment and 4 weeks after each re-treatment.

CONFIDENTIAL
Page 16 of 86

Effective

Effective date:

Title 43QM1903 Clinical Study Protocol - QM1114 - LTS for LCL/GL

Doc id

MA-40372

LIST OF ABBREVIATIONS AND DEFINITIONS OF TERMS

Abbreviation/Term	Definition				
°C	Degrees Celsius				
AE	Adverse Event				
ALP	Alkaline Phosphatase				
ALT/ALAT (SGPT)	Alanine Aminotransferase (Serum Glutamic Pyruvic Transaminase)				
AST/ASAT (SGOT)	Aspartate Aminotransferase (Serum Glutamic Oxaloacetic Transaminase)				
BoNT	Botulinum Toxin				
BoNT-A	Botulinum Toxin Type A				
CFR	Code of Federal Regulations				
CRO	Contract Research Organization				
CSP	Clinical Study Protocol				
CSR	Clinical Study Report				
CTA	Clinical Trial Agreement				
CTN	Clinical Trial Number				
DMP	Data Management Plan				
eCRF	Electronic Case Report Form				
EDC	Electronic Data Capture				
e.g.	For Example (Latin: exempli gratia)				
ET	Early Termination				
EOS	End of Study				
°F	Degrees Fahrenheit				
FDA	Food and Drug Administration				
CCI					
FOCBP	Females of child bearing potential				
FSFV	First Subject First Visit (first subject screened, i.e. who signs the informed consent form)				
FSLV	First Subject Last Visit				
CCI					
GCP	Good Clinical Practice				
GGT	Gamma Glutamyl Transferase				
GL	Glabellar Lines				

Version:

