- 17. The Investigator will administer the treatments. See Section 6.1.6.1 for treatment procedure requirements. Following treatment administration, subjects will be monitored at the study center for 30 minutes. (Section 6.1.6.2)
- 18. Obtain the subject's post-treatment vital signs (blood pressure, heart rate, and respiratory rate). Vital signs are to be taken seated at least 10 minutes after study injections are completed.
- Ask the subject about AEs using an open-ended question. Record all events, as appropriate on the corresponding eCRF form(s).
- Record post-treatment concomitant therapies/procedures.
- 21. Schedule the next visit (Day 7 ±1 day).

•	43QM1903 Clinical Study Protocol - QM1114 - LTS for LCL/GL	Doc id
⊶ GALDERMA	(, (,,,,, .	MA-40372

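### The vital-signs rule in Section 7.2.2 splits Medical History from adverse events by visit rather than by injection, so a first-dose blood pressure, heart rate or respiratory rate abnormality may be missed as a TEAE in cycle 1

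*Protocol*

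**What the plan says.** Section 7.2.2 gives two recording rules for vital signs. For Day 0: "All abnormal values at the baseline visit identified, as clinically significant by the Investigator, shall be recorded in the Medical History form". For later findings: "For any clinically significant changes from the baseline visit, an AE is to be recorded". Both use the baseline visit as the dividing line.

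That visit (Section 8.1.2, Visit 2) contains the first treatment. Vital signs are taken before it and again after it. For the second set, step 18 says: "Vital signs are to be taken seated at least 10 minutes after study injections are completed". Table 1, footnote 4, likewise calls for vital signs before and after treatment. Section 7.2.2 itself refers to the second set just before the Medical History rule: "Vital signs will be taken prior to any blood draw, excluding post-treatment measurements on Day 0".

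The neighbouring rule for the focused physical examination (Section 7.2.1) draws the line at the injection. Findings before it are medical history, and "abnormalities noted post-injection should be recorded as AEs".

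**The concern.** A site that follows 7.2.2 to the letter would enter a clinically significant blood pressure, heart rate or respiratory rate abnormality, first seen shortly after the first dose, on the Medical History form. It would then be recorded as if it had existed before treatment.

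The incidence and severity of TEAEs is a primary endpoint (2.1.1), and all AE analyses are done for the whole study and per cycle (9.1.4). A rule that can divert events in one cycle only affects the comparison between cycles as well as the total. Cycle 1 is the first exposure and the only cycle that every treated subject receives. Analysis could not fully restore a diverted event, because severity, relationship and outcome are collected on the AE form (7.2.5.2.1) and a Medical History entry bypasses it.

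**Working it through.** The protocol gives no figure on this point, so the check sets its provisions side by side.

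1. **Does the Medical History rule stop at the injection?** No. 7.2.2 covers all clinically significant abnormal values at the baseline visit, without a pre-treatment limit.
2. **Does the baseline visit contain a post-injection reading?** Yes: 8.1.2 step 18 and Table 1 footnote 4. 7.2.2 mentions that reading for blood-draw timing but does not exempt it from the Medical History rule.
3. **What do the definitions require?** 7.2.5.1.1 makes a new finding, or a clinically significant worsening, relative to the first visit an AE. 7.2.5.1.2 judges treatment emergence against the pre-treatment state. An abnormality absent before the injection and present after it meets both. Read literally, 7.2.2 sends it elsewhere.
4. **Do the other safety measures share the problem?** No. 7.2.1 splits at the injection. The laboratory rule (7.2.3) also refers to baseline, but its baseline sample is drawn before treatment only, so the wording does no harm there. In Table 1, vital signs are the only physical measurement repeated after the injection on Day 0.
5. **What happens to the same finding after re-treatment?** Vital signs are again taken after the injection (8.1.4). A clinically significant abnormality that is new since Day 0 is then a change from the baseline visit, hence an AE. The two routes differ only for the first dose:

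| Reading | Literal route under 7.2.2 | Route under 7.2.5.1.1 and 7.2.5.1.2 |
|---|---|---|
| Day 0, before injection | Medical History | Not treatment-emergent |
| Day 0, after injection, newly abnormal | Medical History | AE, TEAE |
| After re-treatment, newly abnormal | AE | AE, TEAE |

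6. **How much of the exposure is covered?** With a mean of m treatments per subject, first injections are 1/m of all injections. At the maximum of four treatments for about 900 subjects this is 900/(900 × 4) = 900/3,600 = 25%. At an assumed mean of 2.5 it is 900/2,250 = 40%. These are shares of injections, not of lost events.

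**The case against.** The best defence is that 7.2.2 should not be read alone. Immediately after the post-treatment readings, step 19 of the same visit has the site ask about AEs and record them. AEs are reportable from consent (7.2.5.1.5), whether related or not (7.2.5.2.1). Section 7.2.1 uses the screening and baseline visits as shorthand for pre-injection, and several other sections qualify baseline as prior to treatment. Table 1 schedules no vital signs at screening, which explains why 7.2.2 names the baseline visit for Medical History. The readings themselves are still summarised by visit and cycle (9.1.4).

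Much of this stands: the intended meaning is probably pre-injection, and many sites would record an AE. It does not remove the defect. Step 19 is an open question to the subject, who may not report an abnormal value that causes no symptoms. The definitions are general, whereas 7.2.2 is the specific and mandatory instruction for this measurement. With up to 36 centers, some may follow one and some the other.

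Three stronger readings are tempting, and the protocol does not support them:

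- A reader might infer that acute reactions to the first dose are not counted as TEAEs. The rule touches only three vital-sign measures. Symptomatic reactions reach the AE form through the general AE rules, and even a vital-sign abnormality has a competing route there.
- A reader might infer that the post-injection value becomes part of the analysis baseline. The protocol does not say so, and defining that baseline is commonly left to the SAP. The gap here is only that the recording rule does not say which Day 0 value a change is judged against.
- A reader might attach a count. If 0.5% to 2% of first injections produced such an abnormality, 900 subjects would give 900 × 0.005 = 4.5 to 900 × 0.02 = 18 events. The rate is an assumption without a source in the protocol, and the count treats every event as misfiled. With an unknown misfiled fraction between 0 and 1, this range runs from 0 to 18 and supports no estimate.

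**Conclusion.** The concern holds as a conflict between recording rules. Section 7.2.2, read literally, contradicts 7.2.5.1.1, 7.2.5.1.2 and the injection-based split in 7.2.1 for one reading: vital signs after the first injection on Day 0. The consequence is possible rather than certain: recording that varies between sites, and some TEAEs missed. The direction is clear, since any loss lowers the cycle 1 rate and leaves later cycles untouched. The size cannot be derived, because the protocol gives neither a rate of such abnormalities nor a basis for how sites will read the rule. It is probably small. All analyses are descriptive (9.1.6), so no test or threshold depends on it. The correction is still worth making because the rule feeds a primary endpoint in a study whose primary objective is safety.

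This rests on two assumptions: that at least some sites follow 7.2.2 literally, and that no eCRF instruction outside the protocol already settles the matter.

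**What to change.** Amend 7.2.2 to match 7.2.1:

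- Limit the Medical History sentence to clinically significant abnormal values measured before the Day 0 injection.
- State that clinically significant abnormalities or changes first measured after that injection, on Day 0 or later, are recorded as AEs.
- Name the pre-injection Day 0 value as the reference for change, including for the Day 0 post-treatment reading.

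Carry the same wording into the eCRF guidance, and query any vital-sign Medical History entry dated Day 0 to establish whether the value preceded the injection.

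The cost is about two sentences of protocol text, the guidance update and a data query. No assessment is added. The cycle 1 TEAE rate may rise slightly, because events that could have been filed as history would be counted.
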